## 4. STUDY DESIGN

### 4.1. Overall Design

This is a Phase 2, multi-dose (3.5 mg/kg, not to exceed 170 mg), open-label, single-arm uncontrolled multicenter study of nedosiran in pediatric participants (birth to 11 years of age) with genetically confirmed PH1, PH2, or PH3, with relatively intact renal function based upon eGFR and serum creatinine.

Following the up-to-35-day screening period, participants will return to the clinic for interim visits through Day 180 (6 months). At the discretion of the Investigator, visits on Days 2, 60, 120, and 150 may be conducted in the participant's home, through a combination of telemedicine and home nursing care (at-home telehealth visit). The total time on study for each participant is approximately 7 months. Participants completing this study may be eligible for enrollment into a long-term, open-label, extension study (see Section 6.7).

It is expected that approximately 25 participants will be screened such that approximately 20 participants will complete the study. Participants will receive monthly doses (3.5 mg/kg, not to exceed 170 mg) of nedosiran for 6 months.

Participants with PH3 will only be enrolled if Study DCR-PHXC-104 establishes proof of concept for nedosiran in lowering Uox in participants at least 6 years of age with PH3.

Modeling and simulation (M&S) was performed to determine the dose and dosing frequency for the birth to 5 years of age group in this study based on all available data for participants aged  $\geq 6$  years.

It is expected that the entire trial will have a 24-month duration.

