2.1 Multiplicity Adjustment

Not applicable.

3 Analysis Sets

The following analysis populations are planned for this study:

Participant Analysis Set	Description
Safety Population (SAF)	
The safety population includes all participants who received at least 1 dose of study intervention.
Modified Intent-To-Treat Population (MITT)	
The MITT population includes all participants who received at least 1 dose of study intervention and have at least 1 post-baseline spot urinary oxalate to creatinine ratio. The MITT population is for efficacy analysis.
Evaluable Population (EVAL)	
The evaluable population includes all participants in the MITT population who received 6 full doses of study intervention and completed through the Day 180 Study Visit.
Pharmacokinetic Population (PK)	
The PK population will be defined in PK analysis plan (PKAP).
Per-Protocol Population (PP)	
The PP population includes all PH1 participants who received at least 1 dose of study intervention and had no major protocol deviations that affect efficacy endpoint assessment as adjudicated by the sponsor.
Interim Analysis Population	
The Interim Analysis population includes first 15 PH1 participants who completed the study.

4 Statistical Analyses

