4.1.1.2 Baseline

For all endpoints (except spot urinary oxalate-to-creatinine ratio and annualized stone events rate), the last non-missing observation recorded prior to the first dose of study intervention will be used as the baseline observation for all calculations of change from baseline.

For assessments where the time is not collected (like QoL questionnaires), the last observation recorded prior or during the day of the first dose will be considered as baseline.

For spot urinary oxalate-to-creatinine ratio (including spot urinary oxalate and creatinine measurements), the average of all available spot urine samples (retest samples will be used if available) collected at screening will be used as baseline value.

For annualized stone events rate, baseline will be the number of stone events observed over the past 12 months prior to screening.

Any measure assessed after the date/time of the first dose will be considered as post baseline assessments.

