4.1.1.6 Derived Variables

- Change from baseline = value at current time point – baseline value
- Percentage change from baseline = $\left(\frac{\text{value at current time point} - \text{baseline value}}{\text{baseline value}} \right) * 100\%$
- Spot urinary oxalate-to-creatinine ratio = the average of all the spot urinary oxalate-to-creatinine ratio collected at the specific visit.
- Treatment-emergent AE (TEAE) = any AE with an onset date/time on or after administration (including any partial administration) of the first dose of study intervention and until the study completion date from the end of study CRF.
- Body surface area will be calculated using the following formula (DuBois & DuBois, 1916):
$$BSA = (\text{Weight}^{0.425} \times \text{Height}^{0.725}) \times 0.007184;$$
 with weight in kilograms and height in centimeters.
- Body mass index (BMI) will be calculated using the formula: $\text{Weight [kg]} / (\text{Height}^2 [\text{m}^2])$.
- Estimated Glomerular Filtration Rate (eGFR) will be calculated as described in Protocol Section 8.2.6.1.
- Annualized stone event rate will be derived as number of stone events in the exposure period / total number of years exposed.

The number of stone events will be calculated as the number of discrete (non-concurrent) adverse events marked as a Kidney Stone Event on the adverse event CRF. Kidney stone events include renal stone requiring medical intervention, stone passage with or without hematuria, and renal colic requiring medication.

Concurrent events will be defined as events occurring within the same 4-week (28-day) window. For example, renal colic treated with medication on Monday 12 November 2019 followed by stone passage without hematuria on Friday 30 November 2019 is a single (concurrent) stone event (18 days between start and stop of single stone event). Renal colic treated with medication on Monday 12 November 2019 followed by stone passage without hematuria on Wednesday 13 December 2019 is considered two separate stone events (30 days between discrete event one and event two).

- Quality-of-life Questionnaires:

PedsQL

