4.4 Exploratory Endpoints Analyses

The exploratory efficacy endpoints listed below will be summarized for MITT population and by PH type and age group.

- The percent and absolute change from Baseline in plasma oxalate will be summarized (n, mean, standard deviation, median, minimum, maximum) by visit.
- The change from Baseline in annualized stone event rate will be summarized (n, mean, standard deviation, median, minimum, maximum).
- The change from Baseline in the PedsQL™ will be summarized (n, mean, standard deviation, median, minimum, maximum) by visit.
- The change from Baseline in the WPAI:PH, V2.0, CPV – Caregiver will be summarized (n, mean, standard deviation, median, minimum, maximum) by visit.

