4.8 Changes to Protocol-planned Analyses

Not applicable.

5 Sample size determination

It is expected that approximately 25 participants will be screened, such that approximately 20 participants will complete the Day 180 assessments.

No formal sample size estimations were performed. A sample size of 20 participants was considered sufficient to provide an initial assessment of the efficacy and safety of nedosiran in paediatric participants (birth to 11 years of age) with PH1, PH2 or PH3 and relatively intact renal function.

6 References

3. Uemura O, Nagai T, Ishikura K, Ito S, Hataya H, Gotoh Y, et al. Creatinine-based equation to estimate the glomerular filtration rate in Japanese children and adolescents with chronic kidney disease. Clin Exp Nephrol. 2014a;18(4):626–33.
4. Uemura O, Nagai T, Ishikura K, Ito S, Hataya H, Gotoh Y, et al. Cystatin C-based equation for estimating glomerular filtration rate in Japanese children and adolescents. Clin Exp Nephrol. 2014b;18(5):718-25.
8. Rijnbeek, P. R., et al. New normal limits for the paediatric electrocardiogram. Eur Heart J 2001 22(8): 702-711.

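### The annualized stone rate is averaged per child with no exposure weighting, minimum exposure or defined exposure period, so one event in an early leaver can distort the mean change

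*SAP*

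**What the plan says.** SAP 4.1.1.6 gives the derivation: "Annualized stone event rate will be derived as number of stone events in the exposure period / total number of years exposed". It does not say whether exposure means time between doses, time on treatment or time on study. The same section removes duplicate events: "Concurrent events will be defined as events occurring within the same 4-week (28-day) window".

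SAP 4.1.1.2 sets the comparator: "For annualized stone events rate, baseline will be the number of stone events observed over the past 12 months prior to screening".

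SAP 4.4 gives the analysis set and the statistics: "The exploratory efficacy endpoints listed below will be summarized for MITT population and by PH type and age group", and "The change from Baseline in annualized stone event rate will be summarized (n, mean, standard deviation, median, minimum, maximum".

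MITT (SAP Section 3) requires one dose and that the child "have at least 1 post-baseline spot urinary oxalate to creatinine ratio". It sets no minimum follow-up. The Schedule of Activities (Protocol 1.3) collects spot urine at the Early Termination visit, so a child who leaves before the first monthly visit can still qualify.

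A completer's planned follow-up is about half a year: "participants will return to the clinic for interim visits through Day 180 (6 months" (Protocol 4.1). On numbers, SAP Section 5 says "approximately 25 participants will be screened, such that approximately 20 participants will complete the Day 180 assessments".

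**The concern.** A change from baseline reported with an SD, a median and a range can only be computed from one rate per child. The mean in SAP 4.4 is therefore the plain average of individual rates. A rate based on a few weeks has far greater sampling variance than one based on six months, yet both get the same weight, and the shortest follow-up yields the most extreme non-zero values.

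At stake is how the planned mean and SD for stones are read. With few events and small PH-type and age groups, one event in a child who leaves early could make the mean change look like worsening when events per person-year fell. An undefined denominator also leaves the programmer to choose between readings that give different rates from the same data.

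**Working it through.** The documents give no expected stone rate, dropout rate or sample size calculation for this endpoint, so there is no planned figure to reproduce. Event counts and exit days below are assumptions; the formulas are the SAP's or follow from it.

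**1. What one event is worth.** Rate = 365.25 / days of exposure.

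| Exposure (days) | Rate for one event (per year) | Relative to a 180-day completer |
|---|---|---|
| 14 | 26.09 | 12.9 |
| 30 | 12.18 | 6.0 |
| 60 | 6.09 | 3.0 |
| 90 | 4.06 | 2.0 |
| 180 | 2.03 | 1.0 |

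The definition matters even for a completer: one event is 365.25/180 = 2.03 per year over the whole study, but 365.25/150 = 2.44 if exposure stops at the last dose (Day 150).

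**2. Effect on the on-study mean.** Take 15 PH1 children (the synopsis goal). Fourteen complete 180 days without an event, and one leaves at Day 30 with one event.

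- Unweighted mean: 12.18/15 = 0.81 per year.
- Pooled rate: 1 / [(14 × 180 + 30)/365.25] = 1/6.98 = 0.14 per year.

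With exit at Day 60 or Day 90 the unweighted mean is 0.41 or 0.27, and the pooled rate stays at 0.14. If all 15 complete, both are 0.135 and the gap disappears. In a subgroup of 3 with the same Day-30 leaver, the figures are 12.18/3 = 4.06 and 365.25/390 = 0.94.

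**3. Effect on the change from baseline.** Give the same 15 children 5 baseline events in total over one year each: 5/15 = 0.33 per year.

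- Planned mean change: 0.81 - 0.33 = +0.48 per year.
- Pooled change: 0.14 - 0.33 = -0.19 per year.

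The signs differ here only if the exit is before about Day 73, since 365.25/(15 × 73) = 0.33. For a Day-30 exit they differ when the baseline total is between 3 and 12 events (15 × 0.143 = 2.1; 15 × 0.812 = 12.2).

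**4. Precision.** Assume a common Poisson rate λ, 20 children with 0.5 year and 5 with 30 days (0.082 year).

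- Unweighted: λ × Σ(1/t)/n² = λ × (40 + 60.9)/625 = 0.161λ.
- Pooled: λ/Σt = λ/10.41 = 0.096λ.
- Ratio for the on-study rate: 1.68 (1.67 with 180 days in place of 0.5 year).

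For the change from baseline, an independent one-year count per child adds λ/25 = 0.04λ to both: 0.201/0.136 = 1.48.

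If the five leave at Day 90 instead, the on-study ratio is only 1.08.

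If true rates differ between children, the Day-30 ratio falls. With λ = 1 and an assumed between-child variance of 1 or 4, it is 1.41 or 1.14.

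**The case against.** Several points on the other side are sound.

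- **Status.** The endpoint is tertiary/exploratory, Protocol 9.1 and 9.4.1 plan only descriptive analysis, and SAP Section 2 rules out confirmatory testing. This stands and limits the priority.
- **Other statistics.** SAP 4.4 also reports the median and maximum. The maximum would expose an inflated rate, and the median on-study rate stays at 0 in the scenarios above. This stands, although a median of 0 says little about how often stones occur.
- **Other stone results.** A reader might infer that one early leaver could set the trial's whole stone result. The documents do not support that. SAP 4.3.1.2.1 and 4.5.1 tabulate kidney stone events as adverse events of special interest, by type and severity and with listings. They are not annualized there, so an early leaver's event counts once. What those tables lack is a rate or a comparison with baseline.
- **Dropout.** A reader might infer that five early leavers are expected. The synopsis speaks of about 25 enrolled, but Protocol 4.1 and 9.2 and SAP Section 5 speak of about 25 screened, so the shortfall could be screen failures. Protocol 7.1.1 also keeps children in the study after they stop treatment. Five of 25 is therefore an assumption.
- **Exposure as dosing days.** A reader might take a child with one dose to have one day of exposure, which would inflate rates enormously. Nothing states that reading. The stone count comes from the adverse event form, and the treatment-emergent window in SAP 4.1.1.6 runs to study completion, which points to time on study. The gap is that the SAP does not say so for this endpoint.
- **Bias.** Under a common rate, and with leaving unrelated to stones, the unweighted mean is unbiased and only less precise. It is biased if leaving is related to stone events.
- **Replacing the summary.** Protocol 9.4.4 plans a change from baseline. A pooled rate gives up pairing within child and can be driven by one frequent stone former. This is a good reason not to substitute it.

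**Conclusion.** The point holds at low priority. The plan averages individual annualized rates with no exposure weight, no minimum exposure and no definition of the period, and MITT admits children with short follow-up. One event at 30 days counts six times a completer's event. In the 15-child illustration it turns a fall of 0.19 per year into a mean rise of 0.48.

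That reversal needs an early leaver who also has an event, and it depends on the assumed counts. The precision loss of 1.68 (on-study rate) or 1.48 (change from baseline) needs five Day-30 leavers and a common Poisson rate; it is slight for Day-90 exits and smaller when children differ. With complete follow-up the weighting problem vanishes and only the missing definition remains.

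**What to change.** - **SAP 4.1.1.6:** define time at risk for the stone rate as first dose to last study contact (end-of-study or early-termination visit).
- **SAP 4.4:** keep the planned per-child summary. Add total discrete events divided by total person-years, on study and at baseline, overall and by PH type, with an exact Poisson interval, or one that allows for overdispersion where counts permit. For children under 12 months, baseline person-years should be the length of history actually available, because Protocol 8.1.3.1 accepts a shorter one.
- **Listing:** show each child's exposure beside the per-child rate.

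The cost is a few lines of SAP text and one extra table; dates and events are already collected. Because the pooled rate can be influenced by a frequent stone former, it belongs alongside the per-child summary and should not replace it.

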4.1.1.7 Data Adjustments/Handling/Conventions

All collected data will be presented in listings. Data not subject to analysis according to this plan will not appear in any tables or graphs but will be included in the data listings.

Missing or Partial Dates/Times for Adverse Events (AE) and Prior/Concomitant Medications (CM)

The following list describes how partially missing date information will be handled as it relates to partial or missing AE start dates. Similar rules are applied to handle the missing

dates of prior/concomitant medications. The Partial AE start dates will be imputed as the following:

1. If year is not missing and is after the year of first dose:
 - a. If month is missing, then month will be imputed as January.
 - b. If day is missing, then day will be imputed as the first of the month.
2. If year is not missing and is the same as the year of the first dose:
 - a. If month is missing, then impute the month as the month of the first dose date.
 - b. If day is missing, and the month is the same as the month of the first dose date, then impute day as the day of the first dose date.
 - c. If day is missing but month is after the month of first dose date, then impute day as the first day of the month.
3. If year is missing, then impute the year as the year of the first dose date:
 - a. If month is missing, then impute the month as the month of the first dose date.
 - b. If day is missing, then impute the day as the day of the first dose date.
4. If the start date is completely missing, but the AE is either ongoing or the stop date is after the first dose date then impute the start date as the first dose date.
5. For any cases involving the rules above, if the AE end date is before the AE start date and AE end date is on or after the first dose date, then leave the AE start date missing and assume that AE is treatment emergent for the purpose of the analysis. Further, if the AE stop date is complete and occurs prior to first dose date, leave the AE start date missing and assume that AE is not treatment emergent.

Dates will not be imputed if not considered potentially treatment-emergent. For example, if the AE year matches that of the first dose date but the AE month is prior to that of the first dose date the event is not considered potentially treatment-emergent and no imputed date will be assigned. No imputations will be applied to AE stop dates. No imputations will be applied to AE start or stop times.

Imputation for medication start dates will be handled similarly.

Relationship of the AE to study intervention and intensity will not be imputed for analyses.

Imputation rules in handling the partial or missing Prior/CM end dates are listed below:

1. If the Prior/CM end date year value is missing, the date uncertainty is too high to impute a rational date. Therefore, the imputed Prior/ CM end date will be set to NULL.
2. If the Prior/ CM end date year is not missing and is the same or after the year of first dose date:
 - a. If the Prior/ CM end date month is missing, the imputed end date should be set to the earliest of the 'last treatment follow-up date', '31DecYYYY', and 'date of death'.
 - b. If the Prior/ CM end date day is missing, the imputed end date should be set to the earliest of the 'last treatment follow-up date', 'last day of the month', and 'date of death'.

3. If the imputed Prior/ CM end date is less than the existing Prior/ CM start date, use the Prior/ CM start date as the imputed Prior/ CM end date. Further, if the Prior/ CM end date is complete and occurs after the first dose date, leave the Prior/ CM start date missing and assume that medication is a concomitant medication.

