#### Type of Participant and Disease Characteristics

2. Documented diagnosis of PH1, PH2, or PH3 confirmed by genotyping (historically available genotype information is acceptable for study eligibility).
3. Average spot Uox to creatinine ratio at Screening above 2 times the 95th percentile for age ([Matos et al, 1999](#)):
  - > 0.44 mol/mol in participants < 6 months
  - > 0.34 mol/mol in participants from 6 months to < 12 months
  - > 0.26 mol/mol in participants 12 months to < 2 years
  - > 0.20 mol/mol in participants from 2 to < 3 years and
  - > 0.16 mol/mol in participants from 3 to < 5 years
  - > 0.14 mol/mol in participants from 5 to < 7 years
  - > 0.12 mol/mol in participants from 7 to 11 years
4. Estimated GFR at Screening  $\geq 30$  mL/min normalized to  $1.73 \text{ m}^2$  BSA. See Section [8.2.6.1](#) for equations. For infants aged less than 12 months, serum creatinine below the 97.5th percentile of a healthy population ([Boer et al., 2010](#)).
5. Participants must have been on a stable treatment regimen for PH for 3 months prior to Day 1 and parent(s)/legal guardian should be willing to ensure participant remains on the same stable treatment regimen during the study. Dose adjustments for interval weight gain are acceptable.

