#### 8.3.1. Time Period and Frequency for Collecting AE and SAE Information

All SAEs will be collected from the signing of the ICF until 30 days after the last day of study participation.

All AEs will be collected from the signing of the ICF until the EOS/ET time point specified in the SoA (Section [1.3](#)).

All SAEs will be recorded and reported to the Sponsor or designee immediately and under no circumstance should this exceed 24 hours, as indicated in Section [10.3](#). The Investigator will submit any updated SAE data to the Sponsor within 24 hours of it being available.

Investigators are not obligated to actively seek AE or SAE after conclusion of the study participation. However, if the Investigator learns of any SAE, including a death, at any time after a participant has been discharged from the study, and he/she considers the event to be reasonably related to the study intervention or study participation, the Investigator must promptly notify the Sponsor.

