4.1.4 Demographics and Other Baseline Characteristics

Summary statistics for age, gender, race, ethnicity (where available, as ethnicity may not be collected at all sites), height/length, weight, and BSA will be presented for SAF and by PH type and age group (0-<2, 2 - < 6, 6-<9, and 9 - 11 years). Body mass index and body surface area will be computed as described in Section 4.1.1.6.

Summary statistics will be presented for baseline eGFR, time since PH diagnosis, number of kidney stone events in the last 12 months, and the number of kidney stones at baseline.

These summaries will be conducted for the MITT and SAF populations. All collected demographics and other baseline characteristics will be listed by participant.

The number and percentage of participants reporting various medical histories, grouped by Medical Dictionary for Regulatory Activities (MedDRA) system organ class (SOC) and preferred term (PT) (MedDRA; Version 26.0 or higher), will be tabulated for SAF and by PH type and age group.

Prior medications will be presented separately from concomitant medications. Medications that started prior to dosing on Day 1 will be considered prior medications whether they were stopped prior to Day 1 dosing or not. Missing dates will be handled using the methodology described in Section 4.1.1.7. Medications will be coded using World Health Organization drug dictionary (WHO-DD) version March 2023 or later. The number and percentage of participants reporting prior medication and concomitant medication use, grouped by ATC Level 2 and ATC Level 4, will be tabulated by PH type and age group. This analysis will be conducted for the SAF population. The prior medications and concomitant medications will be provided in a listing.

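### SAP 4.1.1.7 rule 3 gives an adverse event with a known month but no year the first-dose year, so a next-year onset is dated before consent and is not counted as treatment-emergent

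*SAP*

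**What the plan says.** SAP 4.1.1.7 sets out five numbered rules for partial event start dates. Rules 1 and 2 apply when the year is recorded. Rule 3 applies when it is not:

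- Year: "If year is missing, then impute the year as the year of the first dose date".
- Month, only where it too is absent: "If month is missing, then impute the month as the month of the first dose date".
- Day, only where it too is absent: "If day is missing, then impute the day as the day of the first dose date".

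Rule 4 opens "If the start date is completely missing, but the AE is either ongoing or the stop date is after the first dose date" and dates such an event at first dose. Rule 5 has two parts. If the end date is earlier than the imputed start but not earlier than first dose, the start is left missing and the event is assumed treatment-emergent. If a complete stop date is before first dose, the event is assumed not treatment-emergent.

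A closing paragraph withholds imputation from events not considered potentially treatment-emergent. Its example is "if the AE year matches that of the first dose date but the AE month is prior to that of the first dose date".

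SAP 4.1.1.6 requires a treatment-emergent onset to fall from first dose up to study completion. Protocol 8.3.1 states: "All AEs will be collected from the signing of the ICF until the EOS/ET time point".

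Medication start dates are to be handled by similar rules.

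**The concern.** Rule 3 never checks the completed date against the period in which events are collected. Follow-up lasts about six months, so many children will be followed across a year end. For those children the first-dose year can be the wrong year, and a recorded month then places the event well before the child entered the study.

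The outcome also conflicts with the other rules. An event with no start information and a stop date after first dose is kept as treatment-emergent under rule 4. Adding a correct month to the same record removes it. For medication end dates, the same section treats a missing year as too uncertain to impute and leaves the date empty.

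Incidence of treatment-emergent events is a secondary endpoint, and the study is small enough for one misclassified child to show in a table row.

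**Working it through.** The documents give no figure for this point, so the rules were applied directly.

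**Inputs**
- Longest gap from consent to first dose: 35-day screening plus a 14-day extension (protocol 1.1 and 1.3) = 49 days. This assumes consent is not signed before the screening window opens.
- Last visit: Day 180 ± 5 (protocol 1.3), so at latest Day 185.
- Treatment-emergent definition: SAP 4.1.1.6.
- First-dose dates: every day of 2022. Onsets: every day from Day 1 to Day 180, repeated to Day 185. Even spread is an assumption.
- Where the imputed day does not exist in the month, the last day of the month was used (assumption; the SAP is silent).

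**Month and day recorded, year missing.** Suppose the true onset is *k* days after first dose and falls in the next calendar year. Rule 3 moves it back one year, to 365 − *k* days before first dose. With *k* from 1 to 184, that is 364 down to 181 days.

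Example: first dose 15 October 2022, true onset 10 February 2023, so *k* = 118. The imputed date is 10 February 2022, which is 365 − 118 = 247 days before first dose.

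**All four patterns**

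| Start-date parts recorded | Next-year onsets dated before first dose | Days before first dose | Same-year onsets dated before first dose | Imputed date in the example |
|---|---|---|---|---|
| Month and day | 100% | 181 to 364 | 0% | 10 Feb 2022 |
| Month only | 100% | 153 to 334 | 0% | 15 Feb 2022 |
| Day only | about 56% | 1 to 30 | about 45% | 10 Oct 2022 |
| None | 0% | none | 0% | 15 Oct 2022 (first dose) |

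In the first two rows even the smallest shift, 153 days, exceeds the 49-day maximum, so every imputed date precedes consent. In the third row the event can be lost, but the date is not shown to precede consent.

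**Do the other rules recover the first two rows?** Rule 4 needs a completely missing start. The first part of rule 5 needs an end date earlier than the imputed start; an event ending on 14 February 2023 ends after 10 February 2022, and an ongoing event has no end date. The second part needs a stop before first dose. The closing paragraph points the same way as rule 3: once the first-dose year is assumed, an earlier month counts against treatment emergence.

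**The opposite error.** First dose 10 January 2023; screening event from 20 December 2022 to 15 January 2023, year of onset missing. Rule 3 gives 20 December 2023. The end date precedes that start and follows first dose, so rule 5 assumes the event is treatment-emergent. If the event were still ongoing, the imputed date would fall after study completion (Day 185 is 13 July 2023) and it would not count.

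**Share of onset days in the next calendar year.** Over *n* follow-up days, the average of *k*/365 for *k* = 0 to *n* − 1 is (*n* − 1)/730. This gives 179/730 = 24.5% for 180 days and 184/730 = 25.2% for 185.

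**Size of one event.** 1/25 = 4 and 1/20 = 5 percentage points.

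**Medications (rules 2a and 2b, a separate issue).** A background drug recorded only as 2022, with first dose 15 November 2022, takes the first-dose month and then the first-dose day. SAP 4.1.4 says "Medications that started prior to dosing on Day 1 will be considered prior medications", and a start on the first-dose date is not earlier. Yet inclusion criterion 5 reads "Participants must have been on a stable treatment regimen for PH for 3 months prior to Day 1".

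**The case against.** The strongest reply is that the triggering record should hardly ever occur. Events are recorded at Days 1, 2, 15, 30, 45 and 60 and then about monthly, and monitors verify source data (protocol 1.3 and 10.1.6). An event reported at a dated contact has a year that can be worked out. This stands, and it is why the point is minor. It does not make the rule right, because a fallback rule exists for exactly the rare record.

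Some stronger readings are tempting, and the documents do not support them:

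- **Every event with a missing year is lost.** The loss before consent needs a recorded month. With no parts recorded, the start becomes the first-dose date and the event is kept.
- **The rule can only remove events.** The January example shows it adding one.
- **About a quarter of events are misdated.** The 24.5% describes how often follow-up days cross a year end under even enrolment. The error rate also depends on how often the year is missing with the month known, which the documents do not give.
- **The medication default distorts the efficacy results.** SAP 4.5.3 still counts a continuing drug as concomitant, no planned table isolates new starts on treatment, and the primary model has no medication term. Only the prior-medication table changes. The SAP also says the medication rules are similar, not identical.

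**Conclusion.** Rule 3 is wrong as written for an event with a known month and an unknown year. Every next-calendar-year onset of that kind is dated about 5 to 12 months before first dose, always before consent. It leaves the treatment-emergent tables if it is ongoing or stops after first dose. The rule can also class a screening event as treatment-emergent. With only the day recorded, it can date an on-treatment event up to about 30 days early.

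The expected effect on incidence is small. The records should be few, they stay in the listings, and one of them moves a row by 4 to 5 points only if the child has no other qualifying event there. The classification result follows from the SAP text and the 49-day limit; the calendar share alone rests on the even-spread assumption.

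The medication point is lesser still: it understates prior use in one descriptive table. Both corrections are worth making because they are cheap, but neither threatens the study's conclusions.

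**What to change.** Replace rule 3 with:

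> If the year is missing and the month is known, use the year that places the date between ICF signature and study completion; if none or more than one does, leave the start date missing and treat the AE as treatment-emergent unless a complete end date is before the first dose. If year and month are both missing, treat the start date as completely missing (rule 4).

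Once the year is set, rules 1 and 2 can supply a missing day. The collection period is at most 49 + 185 = 234 days, less than a year, so a full month and day can fit only one year. In the enumeration, choosing the year this way recovered the true year for every on-treatment onset with month and day recorded (0 errors).

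For medications add:

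> A medication recorded in the Screening medication history is classed as prior whatever its imputed start date.

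The cost is a few SAP sentences and a small programming change. The downside is that a few pre-dose events with an unknown year may be counted as treatment-emergent, which is the conservative direction for safety.
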